## Statistical Design and Power

The primary outcome for the proposed trial will be weight change from Month 4 to Month 24. This variable will be continuous, and analyses conducted during our team's previous trials have demonstrated that weight change can be well modeled using a normal distribution.³ Thus, standard parametric techniques will be used. A longitudinal mixed model will be used to analyze the primary aim data, using treatment condition and time since study start as fixed effects. One primary contrast of interest will be tested for significance: weight regain between Month 4 and Month 24 in the *ADAPTIVE* vs. *STATIC* treatment conditions. Fixed effects will include randomization condition, time since study start, and initial intervention weight loss (as a binary variable representing whether initial weight loss was ≥10% or <10%, used to stratify randomization). Sensitivity analyses will be conducted to assess robustness of results under alternative assumptions related to missing data (including a missing not-at-random approach assuming that individuals who discontinue participation in the study prior to Month 24 regained an average of .3 kg/month, up to baseline weight³,54,55).

The secondary outcome for the proposed trial will be the proportion of individuals in each group maintaining a clinically-significant ( $\geq 5\%$  weight loss from baseline/Month 0) at Month 24. Percent change will be calculated from assessment weights at Month 0 and Month 24, and participants will be categorized dichotomously as having weight losses at Month 24 of  $\geq 5\%$  or < 5% from baseline. Difference in proportion of participants maintaining a  $\geq 5\%$  weight loss will be assessed using a two-tailed z-test for independent proportions.

As an exploratory aim, we intend to compare weight loss trajectory over time between the two groups. For this, we propose to use longitudinal mixed-effects modeling and the growth curve modeling to analyze weight change data observed at several different time points, where the within-subject data correlated is accommodated by the random-effects terms included in the longitudinal mixed-effects model and by a general covariance matrix in the growth curve model. These analyses will demonstrate differences in weight change between participants in the

*ADAPTIVE* and *STATIC* groups over time. Changes in dietary intake, physical activity, and self-monitoring adherence over time will be assessed using multilevel models for repeated measurements. Potential treatment meditators (e.g., intervention engagement, operationalized as the proportion of possible extended-care sessions attended, adherence to self-monitoring, and changes in dietary intake/physical activity) will be assessed using bootstrapping to estimate confidence intervals around indirect effects. Finally, the rich dataset collected via MyTrack+ (including time-stamped self-monitoring data (including not only frequency counts of self-monitoring behavior but also daily weight, caloric intake, and physical activity data) and ecological momentary assessment questionnaire data collected over a full two year study period) will be used to examine proximal predictors of change in weight and weight-related behaviors. Following the pragmatic framework developed by Nahum-Shani and colleagues, we propose to build dynamic models of weight loss and weight regain, identifying key tailoring variables and potential intervention options for future just-in-time adaptive interventions for weight loss maintenance.

The most recent clinical guidelines for the treatment of obesity (released as a joint report by the American College of Cardiology [ACC], American Heart Association [AHA] and The Obesity Society [TOS]) $^{10}$  define 2.5 kg as the *minimal* amount of weight loss associated with lowered risk of type 2 diabetes, and further note that weight losses of this magnitude are associated with modest improvements in triglycerides, and modest reductions in blood pressure. Thus, similar to previous weight management trials powered to detect this smallest clinically-meaningful difference, $^{3,28}$  sample size for the primary aim analysis was selected to provide a statistical power of .90 to detect a difference in weight change of  $2.5 \pm 5.5$  kg between groups from Month 4 to Month 24. This resulted in an estimated 206 participants (103 participants per group). With SDs of 5.0 and 6.0, estimated power would be .946 and .845, respectively. Assuming a retention rate of 80% at Month 24, 258 participants would need to be randomized at Month 4.

Based on our previous studies, we conservatively estimate that 60% of participants who complete the initial 16-week phone-based behavioral weight loss intervention will be eligible for randomization and ultimately randomized; thus, we propose to recruit 430 adults to take part in the initial weight loss program. Note that this sample size calculation is based on the planned contrast between groups at Month 24. With the observed data collected at the intermediate assessment times before Month 24, the calculated sample size should guarantee enough power for the longitudinal data analyses that include all observed data at different assessment times.

For the secondary aim, we propose to investigate the proportion of participants in each group who achieve a clinically-significant weight loss/maintenance defined by the more conservative Institute of Medicine threshold (≥ 5% from baseline weight). The current ACC/AHA/TOS Clinical Guidelines for the Treatment of Obesity note that maintenance of weight losses of ≥ 5% of baseline weight is associated with not only lower risk of developing type 2 diabetes, but also reductions in HbA1c of 0.6% to 1.0%, reductions in need for diabetes medications, clinically meaningful reductions in fasting glucose, improvements in LDL and HDL cholesterol, reduction in use of lipid-lowering medications, and reductions in systolic and diastolic blood pressure of 3 and 2 mm Hg, respectively. Further, using this cut-off will allow us to compare our results to previous weight loss maintenance trials. Previous trials of phone-based extended-care interventions demonstrate that between 38% and 44% of participants maintain weight losses of ≥ 5% between Months 18 and 24. In assessing sample size needed and power for secondary aim analyses, we assume conservatively that 45% of STATIC participants will maintain clinically-significant weight losses of ≥ 5% at Month 24. Under an intent-totreat approach, including all randomized participants, we will assume any participant not returning for the Month 24 follow-up visit has not met this-cut off. With these assumptions, we assessed necessary sample size to power a 15%, 20%, and 25% difference between achievement of this clinically-significant cut-off in the ADAPTIVE and STATIC conditions. With a sample of 258 randomized participants (the estimated sample size needed to adequately power primary aim analyses), estimated power would be .676 for a 15% difference between ADAPTIVE and STATIC participants (i.e., with 60% and 45% of participants maintaining this clinically-significant cut-off, respectively); power for a 20% difference would be .902 and power for a 25% difference would be .985.

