**Orientation and final eligibility screening.** Participants who meet initial eligibility criteria as assessed via the phone screen will be invited to attend an orientation visit. These visits will be conducted in small groups, and will begin with a discussion of the pros/cons of taking part in research and then discuss specific details of the current study (including but not limited to intervention protocol, the number and timing of follow-up assessment visits, and risks and benefits of taking part in the trial). If social distancing procedures are in effect, the orientation visit will take place by Zoom UFLPHI with e-consenting via REDCap. Potential participants will be given the opportunity to privately ask study staff any remaining questions that they have and then, if they remain interested, will be asked to provide written informed consent.

**Screening Visit.** After signing written informed consent, participants will complete baseline screening measures (see Table 1). If social distancing procedures are in effect, a study-provided scale will be mailed to participants for weight to be measured. At this time, participants will be asked to indicate what days/times they are available to attend intervention groups. Participants will be contacted via phone and informed of their final eligibility. During this call, participants who remain eligible for the initial weight loss program will be informed of their group day/time.

**Baseline (Month 0) Assessment Visit.** The Month 0 assessment visit will take place before the lifestyle weight management program. Once participants have completed baseline measures, they will begin the initial weight loss program.

**Eligibility for the Maintenance Program.** Eligibility for the randomized controlled trial of the *ADAPTIVE* versus *STATIC* maintenance program will be determined after the Month 4 assessment visit. Percent weight change from the Month 0 assessment to the Month 4 assessment will be

calculated; participants who lose ≥ 5% of their Month 0 weight at Month 4 will remain eligible for the maintenance trial.

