Participants will be asked to self-monitor weight daily, using a study-provided BodyTrace scale. Participants will be asked to self-monitor caloric intake and physical activity via the commercial FatSecret mobile app (provided free of charge to participants). This application can be accessed by participants via web (https://www.fatsecret.com/) or via smartphone application. At the first study intervention session, participants will be asked to download this application on their mobile devices and will be guided on how to set up accounts using either their preferred email address or a study-generated email address with no direct link to identifiable information. Participants will then be shown how to use this application to record their body weight, physical activity, and caloric intake each day. Participants will also be given guidance on how to protect their privacy and confidentiality using study devices and smartphone applications (e.g., suggesting using device encryption, using secure passwords and setting up automatic lock screens, and avoiding submitting personally-identifiable information through the applications).

**Randomization.** Participants who successfully achieve weight losses of  $\geq 5\%$  of initial body weight during the initial 16-week weight loss intervention (defined as change in assessment-measured body weight from Month 0 to Month 4) will be eligible for randomization for the maintenance program. After determining eligibility, participants will be randomized using a 1:1 allocation scheme by the study statistician ([name]), stratified by initial weight loss (due to the known association between initial weight loss and longer-term maintenance,  $^{32,33}$  participants will be categorized by whether initial weight loss was  $\geq 10\%$  or < 10%). Participants will be notified of their inclusion/exclusion and asked to return for one in-person study visit to be informed of their randomization (see full description below). This process will take place by phone if social distancing procedures are in effect.

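### Adding continuous Month 0–4 percent weight loss to the primary model, beside the 10% stratum indicator, would gain a little precision at no cost

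*Combined protocol and SAP*

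**What the plan says.** In the combined protocol and SAP, Statistical Design and Power specifies a longitudinal mixed model. Its fixed effects are condition, time since study start, and initial weight loss entered "as a binary variable representing whether initial weight loss was" at least 10% or below 10%. The section identifies this indicator as the stratification variable. It lists no continuous form of initial loss, no Month 4 weight covariate and no covariate-by-time term. The test of interest is stated as "One primary contrast of interest will be tested for significance: weight regain between Month 4 and Month 24" in the two conditions.

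Under Recruitment and Screening, eligibility for the maintenance trial turns on a calculated percentage: "Percent weight change from the Month 0 assessment to the Month 4 assessment will be" computed, and those who lost at least 5% stay eligible. Under Intervention and Randomization, "participants will be randomized using a 1:1 allocation scheme", stratified at 10% initial loss "due to the known association between initial weight loss and longer-term maintenance".

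The sample size is set for "statistical power of .90 to detect a difference in weight change of" 2.5 kg with SD 5.5 kg, giving 103 per group. The plan adds: "With SDs of 5.0 and 6.0, estimated power would be .946 and .845, respectively". Allowing for dropout: "Assuming a retention rate of 80% at Month 24, 258 participants would need to be randomized at Month 4".

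**The concern.** The plan treats initial loss as prognostic and holds it as a percentage for every randomized participant before allocation, yet the model uses only which side of 10% it falls on. Someone who lost 5.1% and someone who lost 9.9% get the same covariate value. If regain varies with initial loss within a stratum, that variation stays in the residual, and the primary confidence interval is wider than it need be. What is at stake is efficiency. The section also does not say whether the model's response is weight at each visit or change in weight, and this decides whether the covariate does anything for the primary contrast.

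**Working it through.** **1. Reproduce the plan's figure.** Inputs from Statistical Design and Power: difference 2.5 kg, SD 5.5 kg, power .90. Alpha is not stated for this test; two-sided .05 is assumed because it reproduces the plan. The two-sample t calculation gives 102.7, so 103 per arm, 206 in all. Power at 103 per arm is .946, .901 and .845 for SD 5.0, 5.5 and 6.0, as stated. 206/.80 = 257.5, so 258 randomized. One-sided .05 gives 83 per arm by the normal approximation and does not match. The calculation is a plain two-group comparison with no covariate.

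**2. How much of the predictor the split keeps.** For a linear relation, the share kept, k, is the squared correlation between percent loss and the 10% indicator. The documents give no distribution of initial loss, so one is assumed: normal, with 60% at or above 5%, truncated at 5%. The 60% borrows the plan's estimate of completers who will be eligible and ultimately randomized. That is not strictly a tail probability, so it serves only as an anchor.

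| SD of initial loss (points) | share at ≥10% | k | lost |
|---|---|---|---|
| 3.5 | .20 | .62 | 38% |
| 4 | .27 | .66 | 34% |
| 5 | .38 | .67 | 33% |

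Other assumed shapes:
- A normal variable split at its median loses 1 − 2/π = 36%.
- A normal with mean 8–10% (the range of typical losses in the Background) and SD 4–5 loses 33–39%.
- Uniform shapes lose 25–39%, and exponential shapes 35–47%.
- If few exceed 10%, more is lost: 47% at SD 3 (13% above the cut) and 81% at SD 2 (2% above).

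**3. Effect on power.** Let r be the correlation between initial loss and Month 4–24 weight change. It is not in the documents, so 0 to .4 is shown. Take 5.5 kg as the unadjusted SD.
- Binary residual SD = 5.5 × √(1 − k r²)
- Continuous residual SD = 5.5 × √(1 − r²)
- Equivalent extra participants = 258 × [(1 − k r²)/(1 − r²) − 1]

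Example, k = .66 and r = .3: binary 5.5 × √(1 − .66 × .09) = 5.33; continuous 5.5 × √.91 = 5.25. The variance falls by 1 − .91/.9406 = 3.3%. Equivalent participants: 258 × (.9406/.91 − 1) = 8.7.

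Over k = .62 to .67, at 103 per arm:

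| r | power, binary | power, continuous | variance reduction | participants of 258 |
|---|---|---|---|---|
| 0 | .901 | .901 | 0 | 0 |
| .1 | .903 | .904 | 0.3–0.4% | about 1 |
| .2 | .908 | .912 | 1.3–1.6% | about 4 |
| .3 | about .917 | .926 | 3.1–3.6% | 8–10 |
| .4 | about .93 | .943 | 5.9–6.8% | 16–19 |

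At r = .4 the wider limits of 25% and 47% lost give 258 × [(1 − .75 × .16)/.84 − 1] = 12 and 258 × [(1 − .53 × .16)/.84 − 1] = 23. At the plan's less favourable SD of 6.0 and r = .4, power is about .88 with the binary covariate and .901 with the continuous one.

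**4. Dependence on the response.** If the response is weight at each visit and the covariate enters as a main effect only, it adds the same amount to a participant's fitted Month 4 and Month 24 weights, so it drops out of the difference. In 10 simulated complete data sets, the estimate and standard error were identical with no covariate, the binary one or the continuous one. If the response is weight change, or covariate-by-time terms are present, the form matters. In simulation at r = .3 with 206 participants, the mean standard error was .758 with none, .737 with binary and .726 with continuous.

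**The case against.** The strongest reply is that nothing is wrong here. Adjusting for the stratification factor as randomized is standard and valid. The estimate is unbiased, type I error is controlled, and chance imbalance within a stratum is already reflected in the standard error. Every binary-adjusted power above is at or over the planned .90. The gain is at most about one point for r of .3 or less and vanishes at r = 0. The plan's association is with longer-term maintenance, which need not equal a correlation with kilograms regained from Month 4. All of this stands, and it limits the point to an efficiency suggestion.

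A reader might infer more, but the documents do not support it:
- **That the trial is underpowered.** The sample size takes no credit for any covariate, so the split takes nothing from it.
- **That a third of the predictor is known to be wasted.** That figure rests on an assumed distribution and a linear relation.
- **That omitting Month 4 weight is an error.** If weights at each visit are the response, Month 4 weight is already in the model.
- **That the primary model has only a random intercept, or that Aim 2 shares the problem.** The section specifies no covariance structure for the primary model, and Aim 2 is an unadjusted two-sample z-test.

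The objection does not remove the core: the continuous value exists for everyone, is fixed before randomization, and costs nothing to use.

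**Conclusion.** The point holds as a free improvement, not as an error in the plan. With normal initial loss, 60% at or above 5% and SD 3.5–5 points, continuous adjustment gains between nothing (r = 0) and about 1.5 power points (r = .4), or about 0 to 19 of the 258 randomized. It also presumes a roughly linear relation and a model form in which the covariate can act on the Month 4–24 contrast. Under the weight-at-each-visit reading with main effects only, neither form of the covariate helps that contrast when data are complete. Stating the response and the visit terms therefore matters as much as replacing the split.

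**What to change.** State whether the response is weight at each visit or change from Month 4. Keep the stratum indicator and add continuous Month 0–4 percent weight loss.
- If the response is weight at each visit, include stratum-by-visit and percent-loss-by-visit terms.
- If the response is change from Month 4, enter percent loss and, optionally, Month 4 weight as covariates with visit interactions.

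In either case, take the treatment test from the condition-by-Month-24 contrast. The cost is a sentence or two of SAP wording, with no new data and no added participants. Settle it before outcomes are compared by arm, so that the choice of covariate form cannot be questioned afterwards.

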# 4. Background:

Obesity remains a substantial public health challenge in the United States. While behavioral lifestyle interventions have been demonstrated to produce weight losses of 8-10% in adults with overweight and obesity, long-term outcomes are suboptimal. Following the end of initial treatment, individuals typically regain 1/3 to 1/2 of lost weight within a year and gradually return to baseline weight in 3-5 years. Research has demonstrated, however, that individuals who are able to continue to adhere to weight management behaviors can successfully maintain their weight loss long-term, implicating non-adherence to the eating and activity changes that produce weight loss as the primary mechanism for this weight regain.

As a result, current clinical guidelines now conceptualize obesity within a chronic disease "continual care" model, necessitating long-term treatment provision. Existing "extended-care" programs typically provide long-term support via monthly sessions (delivered in-person or via telephone) and have demonstrated significant improvements in adherence to behavior change and less weight regain compared to no-contact control. While these effects have been *statistically significant*, the impact of existing programs on weight regain has been *modest* (around 1.5 kg less regain vs. control at 24 months) and there tends to be high individual variability in response to treatment.

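### The only specified missing-not-at-random scenario gives both arms the same regain rate, so it never tests the case where ADAPTIVE dropouts regain more than STATIC dropouts

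*Combined protocol and SAP*

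**What the plan says.** All of the relevant text is in section 6, Statistical Design and Power.

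- Outcome and model: "The primary outcome for the proposed trial will be weight change from Month 4 to Month 24", and "A longitudinal mixed model will be used to analyze the primary aim data".
- Purpose of the extra analyses: "Sensitivity analyses will be conducted to assess robustness of results under alternative assumptions related to missing data".
- The one scenario described: people who stop taking part before Month 24 are assumed to have "regained an average of .3 kg/month, up to baseline weight". No arm is distinguished.
- Planned loss: "Assuming a retention rate of 80% at Month 24". No rate is given by arm.

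The scenario is introduced as one of several sensitivity analyses, but no other is described. The text does not say whether regain runs from Month 4 or from the last observed weight, or whether imputed values are fixed or carry residual variance. No arm-specific, delta-adjusted or tipping-point analysis appears.

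**The concern.** A sensitivity analysis for missing data should move the assumption that could overturn the result. Here that assumption is how ADAPTIVE dropouts compare with STATIC dropouts. Such a difference is plausible. Participants know their assignment (Data and Safety Monitoring Plan). ADAPTIVE calls depend on app, scale and self-monitoring data or on a request, whereas STATIC calls come monthly regardless (Intervention and Randomization). Disengagement may therefore relate to weight differently in the two arms.

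Assigning one common value to both arms pulls the estimated difference toward zero. With similar dropout and fixed values it also shrinks the standard error by about the same factor. A significant result will then usually stay significant, and a report could present that as robustness although the between-arm assumption was never varied.

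**Working it through.** **Inputs.** From Statistical Design and Power: difference 2.5 kg, SD 5.5 kg, 103 per group at Month 24, 258 randomized (129 per group), 80% retention, .3 kg/month, 20 months of follow-up. Assumed because not stated: two-sided alpha of .05, equal dropout unless noted, mean regain in STATIC completers (range shown), imputation variance. Differences are STATIC regain minus ADAPTIVE regain.

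**The plan's own figures.** "sample size for the primary aim analysis was selected to provide a statistical power of .90". A two-sample noncentral t calculation with 103 per group gives power .901 at SD 5.5, .946 at SD 5.0 and .845 at SD 6.0. Retention: 206/.8 = 257.5, so 258. These agree with the plan.

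**Completers only, standing in for the primary result.** Expected completers per arm: 129 × .8 = 103.2. SE = 5.5 × √(2/103.2) = .766, and z = 2.5/.766 = 3.27.

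**The stated scenario, fixed values from Month 4.** Each dropout receives .3 × 20 = 6 kg (cap ignored here). With dropout proportion d:

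- arm mean = (1 − d) × completer mean + d × 6
- arm variance = (1 − d) × 5.5² + d × s² + d(1 − d) × (completer mean − 6)², where s is the SD of the imputed values
- SE = √[(sum of the two arm variances)/129]

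Example with d = .2, s = 0 and completer means of 6 (STATIC) and 3.5 (ADAPTIVE): the difference is .8 × 2.5 = 2.0. The variances are 24.2 and 24.2 + .16 × 6.25 = 25.2. SE = √(49.4/129) = .619 and z = 3.23.

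| Setting | STATIC completer regain | Completer z | z after the scenario |
|---|---|---|---|
| 20% in each arm, fixed values | 2.5 to 8.5 kg | 3.27 | 3.03 to 3.25 |
| 20% in each arm, imputed SD 5.5 | 2.5 to 8.5 kg | 3.27 | 2.75 to 2.91 |
| ADAPTIVE 30%, STATIC 10%, fixed | 2.5 to 6 kg | 3.24 | 1.58 to 2.82 |
| ADAPTIVE 10%, STATIC 30%, fixed | 2.5 to 6 kg | 3.24 | 3.65 to 4.55 |

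In simulations with the baseline-weight cap and either starting point for regain, the significance verdict changed in 0.1% to 4% of trials at 20% in each arm, and in 6% to 56% at 30%/10%.

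**Shift needed to overturn a result.** Let delta be extra regain in ADAPTIVE dropouts beyond what the primary model predicts for them, with no shift in STATIC. The difference becomes D − .2 × delta. Holding the SE at 5.5 × √(2/103) = .766, significance is lost at 1.96 × .766 = 1.50, so delta = (D − 1.50)/.2:

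- D = 2.5: about 5.0 kg
- D = 2.0: about 2.5 kg
- D = 1.75: about 1.2 kg

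**The same question as a rate.** Hold STATIC dropouts at .3 kg/month and raise ADAPTIVE dropouts (fixed values, no cap, STATIC completer regain 4 to 7.25 kg). A 2.5 kg result loses significance at about .47 to .49 kg/month, which is 3.4 to 3.8 kg above STATIC dropouts. The reference point differs: 5.0 kg above the model's prediction is about 2.5 kg above STATIC dropouts, because the model already places ADAPTIVE dropouts 2.5 kg lower. The remaining gap arises because fixed values understate the SE (about .64 to .68 instead of .766). With the cap the effect of the shift is smaller: mean z is 2.14 to 2.39 at .5 kg/month and 1.94 to 2.17 at .6, under assumed weights and losses.

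**Illustrative null case (completer-only).** Suppose ADAPTIVE completers regain 4 kg and dropouts 9 kg, and STATIC regains 5 kg in both. The ADAPTIVE whole-arm mean is .8 × 4 + .2 × 9 = 5 kg, so there is no true difference. Completers show 1.0 kg, z = 1.31. The scenario with fixed 6 kg gives .8/.618, z = 1.30. In simulation ADAPTIVE is favoured significantly in 25.0% and 24.6% of trials, against 2.5% nominal. If half or all dropouts have Month 12 data, the mixed model uses those data and regain runs from the last observed weight, the rates are about 10% to 19% and 7% to 16%, under assumed Month 12 to Month 24 correlations and Month 12 regain.

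**The case against.** The strongest reply is that a completer t-test is not the planned primary analysis. The mixed model uses Month 12 weights, so dropouts seen then inform the estimate. If regain starts from the last observed weight, the scenario also carries forward any between-arm difference seen at Month 12. This stands, and it is why the null-case rates fall. They remain above 2.5%.

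A reader might infer that the scenario cannot show or detect any dependence on missing data. The documents do not support that. Unequal dropout moves z substantially, residual variance lowers it, and the estimate itself falls from 2.5 to 2.0 kg even where z is stable. The list of sensitivity analyses is also open-ended, although nothing else on it is specified.

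A reader might also infer that .3 kg/month is too mild. The Background says "individuals typically regain 1/3 to 1/2 of lost weight within a year", after losses of 8-10%. At an assumed 100 kg that is 8 × 1/3 = 2.7 to 10 × 1/2 = 5.0 kg per year. The scenario's .3 × 12 = 3.6 kg lies inside that range, and the plan cites sources for the rate that cannot be checked here. A central value is a legitimate scenario.

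Finally, the null case is severe: a 5 kg gap between dropouts and completers in one arm and none in the other. It shows the mechanism and is not a forecast.

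**Conclusion.** The point holds in a limited form. The one specified scenario is a weak check on the primary test when dropout is similar in the two arms and fixed values are counted from Month 4. Under any reading of the text it leaves out a difference in regain rate between ADAPTIVE and STATIC dropouts. For a result at the planned effect, the shift needed to overturn it is large (about 5.0 kg beyond the model's prediction). For an observed difference near 1.75 kg it is only about 1.2 kg, and the described analysis would not bring that out.

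The figures rest on a two-sided .05 test, equal 20% dropout, an SE held at the completer value, and assumed completer regain where a range is shown. This is a gap that should be closed before the arms are compared. It is not an error in the primary analysis.

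**What to change.** Keep the .3 kg/month case as one labelled scenario and add a tipping-point analysis:

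- Impute missing Month 24 weights by multiple imputation from the primary mixed model, using Month 12 data.
- Add a regain shift separately by arm, for example 0 to 6 kg in ADAPTIVE with 0 in STATIC, then shifts in both arms.
- Report the shift at which the conclusion changes, with the estimate and interval at each step.
- State whether regain in the .3 kg/month case runs from Month 4 or from the last observed weight, and that imputed values carry residual variance.

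The cost is a short edit to Statistical Design and Power, a little more analysis work and one more table. No new data are needed.

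### Aim 2 is tested without the randomization stratum that Aim 1 adjusts for; a pre-specified stratified test would be a small gain at almost no cost

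*Combined protocol and SAP*

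**What the plan says.** Under Intervention and Randomization, allocation is 1:1 and "stratified by initial weight loss (due to the known association between initial weight loss and longer-term maintenance", with strata cut at a 10% loss. Under Statistical Design and Power, the fixed effects of the Aim 1 mixed model include "initial intervention weight loss (as a binary variable representing whether initial weight loss was ≥10% or <10%, used to stratify randomization".

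The same section gives Aim 2 a single test, with no stratum or covariate: the difference in the proportion of participants maintaining a ≥5% "weight loss will be assessed using a two-tailed z-test for independent proportions". No stratified or adjusted Aim 2 analysis appears elsewhere. All randomized participants are included, and "we will assume any participant not returning for the Month 24 follow-up visit has not met this-cut off". Power is given for the unadjusted comparison only, with 258 randomized and 45% success in STATIC: .676 at a 15-point difference, .902 at 20 and .985 at 25.

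**The concern.** The plan stratifies on initial loss because it predicts maintenance, and adjusts for it in Aim 1. It then leaves it out of Aim 2, which is also a maintenance outcome, and gives no reason.

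The stratum is also tied to the Aim 2 endpoint by definition. Success is a loss of at least 5% from Month 0. A participant who has lost 10% by Month 4 can regain 5% of baseline weight and still succeed, whereas one who has lost 6% fails after regaining a little over 1%. Unless larger initial losers regain much more, success rates will differ by stratum.

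When they differ and the arms are balanced within strata, the unadjusted standard error includes between-stratum variation that the design has already removed. What is at stake is a little precision, a type I error that can drift below its nominal level, and a later choice between adjusted and unadjusted results that nobody has fixed in advance.

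**Working it through.** **Reproducing the stated powers.** The inputs are 129 per arm (258/2) and STATIC 45%, both from Statistical Design and Power, with two-sided alpha .05 (assumed; the plan does not state it). With pooled null variance, power = Φ[(Δ − 1.96·SE₀)/SE₁].

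- 15 points (.45 vs .60): SE₀ = √(2×.525×.475/129) = .0622; SE₁ = √((.2475+.24)/129) = .0615; Φ(.458) = .676.
- 20 points (.45 vs .65): SE₀ = .0619; SE₁ = .0607; Φ(1.295) = .902.
- 25 points (.45 vs .70): SE₀ = .0616; SE₁ = .0596; Φ(2.172) = .985.

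All three agree with the plan.

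**Assumptions for the stratified test.** The documents give no stratum sizes or rates. I take 30% to 50% of participants in the ≥10% stratum, a gap of 10 to 30 points in STATIC success between strata, a common odds ratio, and missing counted as failure.

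The gap range was checked against the plan's SD of 5.5 kg, 80% retention and 45% success. Further assumptions were a baseline weight of 95–105 kg, initial loss normal with mean parameter 8% and SD parameter 3–5% truncated at 5%, and a regain slope on initial loss of 0 to 0.7. The implied gap is about 7 to 30 points.

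**Standard error.** Under the null with balanced strata, the ratio of the stratified to the unadjusted standard error is √(1 − R²), where R² = share×(1 − share)×gap²/(.45×.55).

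- 20-point gap: R² = .21×.04/.2475 = .034 to .25×.04/.2475 = .040, so the standard error is 1.7% to 2.0% smaller.
- 30-point gap: R² = .21×.09/.2475 = .076 to .25×.09/.2475 = .091, so it is 3.9% to 4.7% smaller.

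**Simulation, arms balanced within strata.** There were 200,000 trials per scenario, with no continuity correction. The Monte Carlo SE is about .0005 for type I error and .001 for power.

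| STATIC gap between strata | z-test type I error | Power at 15 points, z | Power at 15 points, CMH | Gain (points) |
|---|---|---|---|---|
| 10 | .050–.051 | no change | no change | 0 |
| 20 | .047–.049 | .690–.692 | .692–.693 | 0.1–0.2 |
| 30 | .042–.043 | .692–.697 | .703–.717 | 1.1–2.1 |

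At a 20-point treatment difference the gain is 0 to 1.0 point. A normal approximation is more generous, at 2.5 to 3.2 points for a 30-point gap and a 15-point difference. I rely on the simulation.

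**Simulation, stratum counts free to vary between arms.** The section on randomization describes no blocking, so this case was run too. Type I error is .051–.053 for the z-test and .049–.051 for CMH. The power change at 15 points runs from −0.6 (10-point gap) to +3.0 (30-point gap).

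**Ceiling on the gap.** With missing counted as failure and 80% retention in each stratum, no stratum can exceed .80. With a 30-point gap, STATIC success in the ≥10% stratum is .45 + .70×.30 = .66 (30% share) or .45 + .50×.30 = .60 (50% share). At a 15-point difference, ADAPTIVE then needs .788 or .745 there, which is .788/.80 = 98.5% or .745/.80 = 93% of those who return. At 20 points it needs .787 to .824, which partly exceeds the cap. A 40-point gap would gain 3.7 to 4.8 points at a 15-point difference but needs .793 to .844. A 30-point gap is therefore about the limit.

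**The case against.** The planned test is valid, its powers are right, Aim 2 is secondary, and at 20 points the plan already reports that "power for a 20% difference would be .902". With balanced strata the gain is essentially zero up to a 20-point gap, and the upper end depends on a gap close to the ceiling. If counts vary freely and the gap is small, CMH loses about half a point, partly because it removes a slight excess in the z-test's type I error. Every input that sets the size is assumed. Aim 1 and Aim 2 also have different outcomes and models, so using different methods is not a contradiction.

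All of that stands, and it keeps this an optional improvement. Two things remain. First, across these scenarios the CMH test holds its level at .048 to .052 whether or not strata are balanced, while the z-test's level moves between .042 and .053. Second, nothing in the plan explains why a factor chosen for its link to maintenance is dropped for a maintenance endpoint.

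**Conclusion.** The concern holds as a minor efficiency and consistency point. The Aim 2 test does not use the stratum on which participants are randomized. Using it would change power at a 15-point difference by 0 to about 2 points with balanced strata, or by −0.6 to +3.0 points with free counts. The z-test is mildly conservative only with balanced strata and a gap of about 20 points or more.

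These figures assume 30% to 50% of participants in the ≥10% stratum, a 10- to 30-point gap in STATIC success, a common odds ratio and 129 per arm. Stratification does not rescue the 15-point case, where power stays near .70.

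**What to change.** Name one stratified analysis as the Aim 2 test: a CMH test (no continuity correction) on the randomization stratum, with a Mantel-Haenszel risk difference and confidence interval. Keep the planned population of all randomized participants, with missing Month 24 weight counted as failure. Report the raw proportions by arm, and keep the z-test as a sensitivity analysis. The risk difference stays on the scale the plan already uses; a logistic model would change the target to a conditional odds ratio.

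Label the stated powers as those of the unadjusted test, or recompute them under stated stratum rates. The cost is two or three sentences, fixed before outcome data are seen. The stratum is known for everyone at randomization, so no new data are needed.
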